3.2 Effectiveness Analysis Set

The subjects below shall be excluded from effectiveness analysis set in the following order:

- (1) Subjects who excluded from safety analysis set
- (2) Missing HbA1c value at both baseline and after administration of Trajent

4. Endpoints

4.1 Effectiveness Endpoints

- Glycosylated hemoglobin (HbA1c)
- Fasting plasma glucose (FPG)
- Final effectiveness assessment

	CONFIDENTIAL :	Last Update Date
	THIS DOCUMENT AND INFORMATION CONTAINED HEREIN IS PROPRIETARY TO COMPANY AND IS NOT TO BE DISCLOSED WITHOUT THE WRITTEN PERMISSION OF COMPANY.	21-AUG-2017
STATISTICAL ANALYSIS PLAN(V3.0)		

4.2 Safety Endpoint

- The incidence proportion of all AEs

5. Assessment Criteria

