5. VARIABLES AND THEIR ASSESSMENT

5.1 SAFETY

5.1.1 Endpoint(s) of safety

All reported adverse events including hypoglycemic events in patients who take at least one dose of Trajenta will be noted.

Hypoglycemic events include the overall hypoglycemic events, symptomatic hypoglycemia, confirmed hypoglycemia, nocturnal hypoglycemia, and severe hypoglycemia.

Endpoints pertaining to safety will be presented as incidence rates of adverse events and will include:

- adverse events
- unexpected adverse events
- serious adverse events
- drug-related adverse events
- adverse events leading to discontinuation
- adverse events by intensity, outcome of the event, causality

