6.1 Demographics and Baseline Characteristics

Data for the demographics and baseline characteristics in safety analysis set is demonstrated by descriptive statistics. In the descriptive statistics, number of subjects, mean, standard deviation, median, minimum and maximum will be calculated for continuous variables, and frequency and percentage will be presented for categorical variables.

The following demographics and baseline characteristics will be reported.

< Demographic information >

- Age, Gender, Pregnancy, Allergy, Height, Weight, Waist circumference, Smoking status, Diabetes mellitus complications and their classification, Other medical history and its classification, duration of T2DM, Family history, Pediatric group (Under 19 years), Geriatric group (65 years or older), Kidney disorder, Liver disorder, Subjects whose drug administration period of long-term (24 weeks or more)

< Medication information >

- Concomitant medication and its classification, Trajenta administration status (Total administration period of Trajenta, Total administration dose of Trajenta), Reason of prematurely study withdrawal, Other anti-diabetic agent and its classification

	CONFIDENTIAL :	Last Update Date
	THIS DOCUMENT AND INFORMATION CONTAINED HEREIN IS PROPRIETARY TO COMPANY AND IS NOT TO BE DISCLOSED WITHOUT THE WRITTEN PERMISSION OF COMPANY.	21-AUG-2017
STATISTICAL ANALYSIS PLAN(V3.0)		

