6.3 Safety Analyses

In the safety analysis set, the number of subjects with AEs and the number of AEs will be calculated. Also, the incidence proportion of AEs will be estimated with its 95% confidence interval.

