6.3.1 Adverse Events by Demographics and Baseline Characteristics

For the AE(s) by demographics and baseline characteristics in the safety analysis set:

- The number of subjects to whom AE occurred and the number of AEs will be calculated.
- The incidence proportion of AEs and its 95% confidence interval will be estimated. Chi-square test or Fisher's exact test will be used for comparing between subcategories of each demographics and baseline characteristics.
- If necessary, analysis for the impact of the safety may be carried out using logistic multiple regression analysis. In general, the variables corresponding to the baseline characteristics listed in section 6.1 are used as an independent variable. However, as considering the structure and characteristics of the collected data, the variables used for the actual analysis can be added or subtracted.

	CONFIDENTIAL :	Last Update Date
	THIS DOCUMENT AND INFORMATION CONTAINED HEREIN IS PROPRIETARY TO COMPANY AND IS NOT TO BE DISCLOSED WITHOUT THE WRITTEN PERMISSION OF COMPANY.	21-AUG-2017
STATISTICAL ANALYSIS PLAN(V3.0)		

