6.3.2 Adverse Events by Preferred Terms

All AEs recorded in the CRF will be classified by body organs and terms under the classification standard of MedDRA terms, and all AEs excluding the AEs where causal relationship with Trajenta is “Unlikely” will be treated as AEs which causality cannot be excluded (hereafter “Adverse Drug Reaction(ADR)”).

For subjects to whom AE occurred, the incidence proportion of AEs and the number of AEs will be summarized.

Details are as follows.

- ① The frequency and percentage of the number of AEs according to serious adverse event, intensity, outcome of the event, action taken, causality, therapy of the event will be calculated.
- ② All AEs will be classified into the preferred terms according to serious adverse event, intensity, outcome of the event, action taken, causality, therapy of the event. The frequency and percentage of the number of each AE will also be calculated.
- ③ The number of subjects and the number of AE/ADR, Serious AE/Serious ADR, unexpected AE/ADR, unexpected Serious AE/unexpected Serious ADR will be calculated according to the preferred terms. In this case, the following subgroups are presented separately. Also, the incidence proportion and its 95% confidence interval will be estimated.
 - All of safety analysis set
 - Short-term effectiveness analysis set (Administration of Trajenta less than 24 weeks)
 - Long-term effectiveness analysis set (Administration of Trajenta for 24 weeks or more)
 - Subjects in effectiveness analysis set who administered DPP-4 inhibitor before administration of Trajenta
 - Subjects in effectiveness analysis set who did not administer DPP-4 inhibitor before administration of Trajenta
- ④ Preferred terms of Serious AE/Serious ADR, unexpected AE/ADR will be presented respectively according to the proportion of AE in the local product document.
- ⑤ For subjects excluded from the safety analysis set[†], the number of subjects and the number of AE/ADR, Serious AE/Serious ADR, unexpected AE/ADR, unexpected Serious AE/unexpected Serious ADR will be calculated according to the preferred terms. Also, the incidence proportion and its 95% confidence interval will be estimated.

[†]Subject excluded from safety analysis set: ‘Subjects who have not taken Trajenta’ and ‘Follow-up failure’ of patients excluded from safety analysis sets will be excluded (Reflecting the Ministry of Food and Drug Safety (MFDS) guideline).

	CONFIDENTIAL :	Last Update Date

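### The SAP tests crude AE proportions across length of Trajenta administration, a post-baseline variable, so the short- versus long-term contrast can mislead in either direction

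*SAP*

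**What the plan says.** The protocol (5.1.1, repeated in the synopsis) states: "Endpoints pertaining to safety will be presented as incidence rates of adverse events". It gives no denominator or unit. The SAP endpoint (4.2) is "The incidence proportion of all AEs", and under SAP 6.3 "the incidence proportion of AEs will be estimated with its 95% confidence interval". No person-time denominator, exposure-adjusted rate or time-to-event analysis appears in the SAP.

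SAP 6.1 lists "Subjects whose drug administration period of long-term (24 weeks or more") and, under medication information, the total administration period, all under the title of demographics and baseline characteristics. For AE proportions, SAP 6.3.1 says that a chi-square or Fisher's exact test "will be used for comparing between subcategories of each demographics and baseline characteristics". It also allows a logistic regression that generally takes its independent variables from the 6.1 list. SAP section 8 sets a two-sided 0.05 level for all tests.

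SAP 6.3.2 then presents AE, ADR and serious-event proportions with 95% confidence intervals for the "Short-term effectiveness analysis set (Administration of Trajenta less than 24 weeks") and the "Long-term effectiveness analysis set (Administration of Trajenta for 24 weeks or more"); SAP 7.4 lists the matching tables. No test is specified for these tables. (6.3.2 labels the groups as effectiveness sets, while 7.4 places them in the safety set. That label also needs settling, but it is a separate matter.)

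**The concern.** A patient's length of administration is an outcome of the treatment course, not a characteristic at entry. Two mechanisms then act on a crude proportion, in opposite directions:

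- **Time at risk.** If AE observation ends soon after treatment ends, patients with short administration have had less time to report an AE. Their proportion is lower at the same underlying risk.
- **AEs deciding the group.** A patient who stops because of an AE is placed in the short group by that AE. This raises the short group's proportion and lowers the long group's.

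Safety is the study's primary objective. A significant result from the 6.3.1 test, or a visible gap in the 6.3.2 table, could be read as a signal in one group or as reassurance in the other when the risk is the same in both. Absence of a gap would be no more informative, because the two mechanisms can cancel.

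**Working it through.** **Is there a figure to reproduce?** No. The documents state no AE rate, no share of patients under 24 weeks and no power calculation. The 3,000 patients are a regulatory requirement (Protocol 7.6). What follows is an illustration.

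**Inputs from the documents.** N = 3,000; planned follow-up 24±2 weeks for everyone (Protocol 7.6); AE collection to 7 days after the last follow-up visit (Protocol 5.1.2.2); cut at 24 weeks (SAP 6.1, 6.3.2); two-sided 0.05 (SAP section 8).

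**Assumed inputs.** A constant AE hazard L, the same for all patients; the typical exposure in the short group; the share of patients in it; the share of patients with an AE who stop because of it.

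**Step 1: time at risk alone.** Assume observation ends one week after the last dose. The expected proportion is p = 1 − exp(−L × (weeks + 1)/52.18). With L = 0.25:

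- 12 weeks: 1 − exp(−0.25 × 13/52.18) = 6.0%
- 24 weeks: 1 − exp(−0.25 × 25/52.18) = 11.3%

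**Step 2: chance of a significant test when the hazards are equal.** Use Φ[(|p2 − p1| − 1.96 × SE0)/SE1], with SE0 pooled and SE1 unpooled. With 20% in the short group (600 versus 2,400), p1 = 6.04% and p2 = 11.29%, the pooled proportion is 10.24%, SE0 = 0.01384 and SE1 = 0.01168. The argument is (0.0525 − 0.0271)/0.01168 = 2.17, which gives 98.5%.

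At L = 0.25 against 24 weeks, with 20% in the short group:

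| Short exposure | Short | Long | Long/short ratio | Chance of p < 0.05 |
|---|---|---|---|---|
| 6 weeks | 3.3% | 11.3% | 3.42 | >99.9% |
| 12 weeks | 6.0% | 11.3% | 1.87 | 98.5% |
| 18 weeks | 8.7% | 11.3% | 1.30 | 44% |
| 22 weeks | 10.4% | 11.3% | 1.08 | 8% |

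For 12 weeks, L = 0.10 gives 2.5% versus 4.7% (chance 71%) and L = 0.50 gives 11.7% versus 21.3% (>99.9%). Over short shares of 10% to 30% and these three hazards, the chance runs from 40% to >99.9% for 12 weeks, but only from 4% to 15% for 22 weeks.

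**Step 3: let AEs cause stopping.** Keep L = 0.25 for everyone. Let 15% stop for unrelated reasons at a uniformly distributed time in weeks 0–24, and let a share d of patients with an AE stop at its onset. For simplicity, observation now ends at stopping, without the extra week. The 24-week risk is p = 1 − exp(−0.25 × 24/52.18) = 0.1086. The risk before a uniform stopping time is q = 1 − p/h with h = 0.25 × 24/52.18 = 0.1150, so q = 0.0554.

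- Short = (0.85·p·d + 0.15·q)/(0.85·p·d + 0.15)
- Long = p(1 − d)/(1 − p·d)

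| d | Short | Long |
|---|---|---|
| 0 | 5.5% | 10.9% |
| 10% | 0.01754/0.15923 = 11.0% | 9.9% |
| 30% | 0.03600/0.17770 = 20.3% | 7.9% |

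The hazard never changes, yet the contrast goes from a twofold deficit in the short group, through near equality, to an excess of about 2.6-fold.

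**Step 4: would patient-years within the two groups repair it?** Under the same model with d = 10%, first-event rates per patient-year are 0.50 (short) and 0.23 (long), although the true value is 0.25 for all. The crude proportions in that case were nearly equal, so dividing by person-time makes this contrast worse. Over the whole set, the rate is 0.25 at every d.

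**The case against.** Several objections have force.

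**The protocol's wording.** A reader might infer that the protocol committed to person-time rates and that the SAP broke the commitment. The documents do not support that. The protocol never defines its term, and the SAP itself uses rate for plain percentages (achievement rate in 5.1, effectiveness rate in 6.2). This is a term to define.

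**Follow-up is the same for all.** A reader might also infer that exposure differs by study design. It does not: every patient is enrolled for 24±2 weeks in a single arm. Differences come from early stopping, the visit window and the SAP's cut. A patient whose treatment record ends at an on-schedule visit in week 22 or 23 counts as short-term, and the table shows how small the time effect is there.

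**Administration time is not observation time.** AEs are collected to 7 days after the last follow-up visit, and patients with incomplete safety follow-up leave the safety set (SAP 3.1). Someone who stops early may still be observed to week 24, so Step 1 need not apply. This stands, but it removes only the first mechanism. In the Step 3 model with everyone observed for 24 weeks and d = 30%, the short group would show (0.85 × 0.1086 × 0.3 + 0.15 × 0.1086)/0.1777 = 24.8%, against 7.9% in the long group.

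**The study is descriptive.** Protocol 7.1 and 7.2 specify no confirmatory hypotheses, and no test is attached to the 6.3.2 tables. This limits the consequences. It does not make the 6.3.1 test interpretable.

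**Conclusion.** The point holds for comparisons of AE proportions across length of administration: the tests and possible model covariates in SAP 6.3.1, and the reading of the short/long tables in 6.3.2 and 7.4. Followed as written, the SAP compares AE risk across a variable that partly measures time at risk and is partly determined by AEs.

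Neither the size nor the direction of the distortion can be known from the documents. Under assumed equal hazards, the long/short ratio runs from about 1.08 (short exposure near 22 weeks) to 1.8–1.9 (12 weeks) and 3.3–3.5 (6 weeks). It falls below 1 once enough AEs lead to stopping. All of this rests on a constant hazard and on assumed exposure times, group shares and stopping behaviour.

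A reader might go further and conclude that the overall AE proportion is diluted by short-exposure patients and so unsound. The documents do not support that: the proportion over a planned 24-week observation is an acceptable descriptive figure. The change should be made because it is cheap and prevents a misleading table. It does not call the main safety estimate into question.

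**What to change.** 1. Remove total administration period and the 24-week indicator from the AE significance tests and from the logistic model covariates in SAP 6.3.1. Total dose and reason for premature withdrawal are on the same 6.1 list and are also post-baseline, so they should be considered at the same time.
2. Keep any short/long AE table that the regulator expects, as description only, with a note that it does not compare risk.
3. To describe early versus later risk, report AE, ADR and SAE incidence in fixed intervals, for example weeks 0–12 and 12–24, among patients still under observation at the start of each. AE onset (Protocol 8.4.2) and visit dates (Protocol 6.2.2.1 to 6.2.2.3) are already recorded.
4. Beside the overall proportion, report one rate per 100 patient-years with a 95% confidence interval for the whole safety set. Person-time should end at the first event or at the end of AE observation, which is not the same as the administration period already derived. Define incidence rate and incidence proportion once and use them consistently in both documents.

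Patient-year rates within the short and long groups should not be used as the remedy, because an AE can decide which group a patient is in (Step 4).

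The cost is minor extra programming and the loss of an exploratory comparison. No new data collection is needed.

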5.1 Effectiveness Assessment Criteria

- The change from baseline to last visit[†] of HbA1c
- Achievement rate of target effectiveness (HbA1c of < 6.5% at last visit)
- Achievement rate for target of reduction (At least 0.5% HbA1c lowering at last visit)
- The change from baseline to last visit of FPG
- Final effectiveness assessment

Defines the final effectiveness assessment (Improved, No changed, Worsened, Uevaluable) based on both HbA1c and FPG that measured at baseline and last visit. The final effectiveness assessment is as the following criteria:

- Improved: In case the symptoms, such as symptoms of improvement or maintenance[†], are judged
 - I. In the last visit compared to the baseline, in case the both HbA1c and FPG are maintained or decreased
 - II. In the last visit compared to the baseline, in case the HbA1c is maintained or decreased and the FPG is increased
 - III. In the last visit compared to the baseline, in case the HbA1c is increased and the FPG is maintained or decreased
- No changed: In case there is no significant change between baseline and last visit, that is, in case it is not judged to be maintenance effect
 - I. In the last visit compared to the baseline, in case the HbA1c is increased, but the FPG is unknown
- Worsened: In case the symptoms are worse in the last visit compared to the baseline
 - I. In the last visit compared to the baseline, in case the both HbA1c and FPG are increased
- Not evaluable: In case the collected information is insufficient and the final effectiveness

	CONFIDENTIAL :	Last Update Date
	THIS DOCUMENT AND INFORMATION CONTAINED HEREIN IS PROPRIETARY TO COMPANY AND IS NOT TO BE DISCLOSED WITHOUT THE WRITTEN PERMISSION OF COMPANY.	21-AUG-2017
STATISTICAL ANALYSIS PLAN(V3.0)		

assessment can not be classified as 'Improved', 'No changed' or 'Worsened'

† Maintenance: In case the symptoms are likely to worsen when the administration of Trajenta is interrupt, or, in case the same effect is continue when replacing to existing drugs, etc.

‡ Last visit: The last visit point that measured HbA1c after administration of Trajenta

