Proprietary confidential information. © 2017 Boehringer Ingelheim International GmbH or one or more of its affiliated companies.

Name of company/Marketing Authorisation Holder: Boehringer Ingelheim Korea		Tabulated Study Protocol	
Name of finished product: Trajenta			
Name of active ingredient: Linagliptin			
Protocol date: 1 December 2011	Trial number: 1218.104/UXX-XXXX		Revision date: 22 Feb 2017
Duration of treatment:	1) Treatment duration for short-term surveillance: 12±2 weeks, long-term surveillance: 24±2 weeks. 2) Study duration: 6 years. (KFDA set Trajenta re-examination period from 14 Sep 2011 to 13 Sep 2017. Interim report planned biannually for the initial two years and annually thereafter by Dec 2017.)		
Criteria for effectiveness:	1. Main endpoint 1) Change from baseline in HbA1c after 24 weeks of treatment. 2. Other endpoint 1) Occurrence of treat to target effectiveness response, that is an HbA1c under treatment of < 6.5% after 24 weeks of treatment. 2) Occurrence of relative effectiveness response (HbA _{1c} lowering by at least 0.5% after 24 weeks) 3) Change from baseline in fasting plasma glucose (FPG) after 24 weeks of treatment		
Criteria for safety:	All reported adverse events including hypoglycemic events in patients who take at least one dose of Trajenta will be noted. Endpoints pertaining to safety will be presented as incidence rates of adverse events		
Statistical methods:	Descriptive statistics		

FLOW CHART

Data points	Baseline	Follow-up 1	Follow-up 2
Visit Number	1	2	3
Week/s	0	12±2	24±2
Diagnosis	X		
Inclusion / exclusion criteria	X		
Demographics	X		
Diabetes mellitus complications	X		
Other medical history	X		
Anti-hyperglycemic agents	X	X	X
Concomitant medications	X	X	X
Trajenta administration status	X	X	X
Renal function	X [^]		
Effectiveness endpoints	X	X	X
Changes in lab tests		X [^]	X [^]
Adverse events		X	X
Study completion		X	X

[^]: If applicable.

TABLE OF CONTENTS

TITLE PAGE	오류! 책갈피가 정의되어 있지 않습니다.
NON-INTERVENTIONAL STUDY PROTOCOL SYNOPSIS	2
FLOW CHART	4
TABLE OF CONTENTS	5
ABBREVIATIONS	8
1. INTRODUCTION	9
1.1 MEDICAL BACKGROUND	9
1.2 DRUG PROFILE	9
2. RATIONALE, OBJECTIVES, AND BENEFIT-RISK ASSESSMENT	10
2.1 RATIONALE FOR PERFORMING THE STUDY	10
2.2 STUDY OBJECTIVES	10
2.2.1 Primary objective	10
2.2.2 Secondary objective	10
2.3 BENEFIT-RISK ASSESSMENT	10
3. DESCRIPTION OF DESIGN AND STUDY POPULATION	11
3.1 OVERALL DESIGN AND PLAN	11
3.1.1 Administrative structure of the study	11

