3.3.2 Inclusion criteria

- Patients who have been started on Trajenta in accordance with the approved label in Korea
- Patients who have signed on the data release consent form

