5.2 EFFECTIVENESS

5.2.1 Endpoint(s) of effectiveness

The main effectiveness endpoint in this study is the change from baseline in HbA_{1c} after 24 weeks of treatment.

The other effectiveness endpoints are the following:

- Occurrence of treat to target effectiveness response, that is an HbA_{1c} under treatment of < 6.5% after 24 weeks of treatment.
- Occurrence of relative effectiveness response (HbA_{1c} lowering by at least 0.5% after 24 weeks)
- Change from baseline in fasting plasma glucose (FPG) after 24 weeks of treatment

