6.5% at last visit and whose HbA1c lowering is at least 0.5% at last visit will be calculated. Additionally, the difference of FPG between baseline and last visit shall be analyzed with paired t-test.

- ① All of effectiveness analysis set
- ② Short-term effectiveness analysis set (Administration of Tragenta less than 24 weeks)
- ③ Long-term effectiveness analysis set (Administration of Tragenta for 24 weeks or more)
- ④ Subjects in effectiveness analysis set who administered DPP-4 inhibitor before administration of Tragenta
- ⑤ Subjects in effectiveness analysis set who did not administer DPP-4 inhibitor before administration of Tragenta

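### The HbA1c <6.5% achievement rate sets no condition on baseline HbA1c, so it can count patients already below 6.5% before Trajenta as reaching target

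*SAP*

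**What the plan says.** Protocol section 5.2.1 lists among the other effectiveness endpoints "Occurrence of treat to target effectiveness response", and the synopsis gives it in full: "Occurrence of treat to target effectiveness response, that is an HbA1c under treatment of < 6.5% after 24 weeks of treatment". SAP section 5.1 carries it forward as "Achievement rate of target effectiveness (HbA1c of < 6.5% at last visit"). Both definitions look only at the value on treatment.

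SAP section 6.2 states the calculation: the frequency and percentage of patients below "6.5% at last visit and whose HbA1c lowering is at least 0.5% at last visit will be calculated". It does so for five groups. The first is "All of effectiveness analysis set"; two split by treatment duration at 24 weeks; two split by earlier DPP-4 inhibitor use, one of them being "Subjects in effectiveness analysis set who administered DPP-4 inhibitor before administration of Tragenta".

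No rule elsewhere removes patients who start below 6.5%:
- Protocol section 3.3.2 admits "Patients who have been started on Trajenta in accordance with the approved label in Korea", with signed data release consent. Section 3.3.3 excludes only previous Trajenta exposure and current trial participation. Neither sets an HbA1c floor.
- The safety-set exclusions in SAP section 3.1 do not mention HbA1c.
- The only HbA1c-based exclusion in SAP section 3.2 is "Missing HbA1c value at both baseline and after administration of Trajent".

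**The concern.** The names given to this measure, a treat-to-target response in the protocol and an achievement rate in the SAP, invite the reading that these patients reached target on Trajenta. A patient at 6.3% before the first dose and 6.3% at last visit counts the same as one who fell from 7.4% to 6.3%. Target kept and target reached are merged.

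A reader of the planned output could not separate them. Baseline HbA1c is not among the characteristics in SAP section 6.1 or the tables in section 7.2, and no planned table shows how many patients began below 6.5%. The optional multiple regression in section 6.2 models the change in HbA1c, not this rate.

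The rate therefore depends partly on who was enrolled. That also applies to the percentages shown side by side for patients with and without earlier DPP-4 inhibitor use: they may differ because the groups began with different shares already below 6.5%.

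**Working it through.** The documents state no expected target rate and no baseline HbA1c distribution, so there is no figure of theirs to reproduce. The structure follows from the definition; the size rests on assumptions.

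**Inputs.** From the documents: the threshold (<6.5%), the absence of a baseline condition, and the planned 3,000 patients (Protocol section 7.6). Assumed: b = 5–20%, s = 80–90%, c = 20–30%, where
- b = share with baseline HbA1c below 6.5%,
- s = share of those still below 6.5% at last visit,
- c = share of patients with baseline of at least 6.5% who are below 6.5% at last visit.

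**Formula.** With both HbA1c values known, planned rate = b × s + (1 − b) × c. Subtracting c gives the excess, b × (s − c). It is zero if b = 0 or s = c, and positive when b > 0 and s > c.

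| b | s | c | Planned rate | Excess over c |
|---|---|---|---|---|
| 5% | 80% | 20% | 0.040 + 0.190 = 23.0% | 3.0 points |
| 20% | 90% | 20% | 0.180 + 0.160 = 34.0% | 14.0 points |
| 5% | 80% | 30% | 0.040 + 0.285 = 32.5% | 2.5 points |
| 20% | 90% | 30% | 0.180 + 0.240 = 42.0% | 12.0 points |

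The excess runs from 0.05 × (0.80 − 0.30) = 2.5 points to 0.20 × (0.90 − 0.20) = 14 points. A wider set of assumptions (b = 5–30%, s = 70–95%, c = 15–30%) gives 0.05 × (0.70 − 0.30) = 2 points to 0.30 × (0.95 − 0.15) = 24 points.

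**In patients.** Take b = 10%, s = 85%, c = 30% and all 3,000 evaluable. Then 3,000 × 0.10 × 0.85 = 255 stayed below 6.5% and 3,000 × 0.90 × 0.30 = 810 reached it. The planned rate is 1,065/3,000 = 35.5%, against 30.0% among those not at target at baseline. Of the counted achievers, 255/1,065 = 24% were below 6.5% before Trajenta.

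**Two groups side by side.** Suppose conversion is 25% and s = 85% in both DPP-4 inhibitor groups, but 20% of prior users and 5% of non-users start below 6.5%. The table would show 0.20 × 0.85 + 0.80 × 0.25 = 37% against 0.05 × 0.85 + 0.95 × 0.25 = 28%. The 9-point gap comes from baseline mix alone. These inputs are also assumed.

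**Denominator.** The exclusion in SAP section 3.2 can be read as keeping patients who lack only one of the two values. Those without a baseline value cannot be classified. Those without a later value would lower the rate if left in the denominator.

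**The case against.** The strongest defence is that, as regards baseline, the SAP does what the protocol asks. The protocol defines a status on treatment, and the share below 6.5% at last visit describes that status correctly. This stands: the number is not wrong, and the endpoint should not be replaced. What is missing is the information needed to read it as target reached.

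SAP section 5.1 also counts maintenance as a good outcome in its final effectiveness assessment, including an effect that continues when existing drugs are replaced. So keeping control after a switch is not nothing. But that definition belongs to the final assessment; the 6.5% rate does not separate kept from reached.

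Other measures soften the problem. The paired HbA1c change does not have it, and the companion response requires a fall of at least 0.5%, so starting low earns no credit there. The group without earlier DPP-4 inhibitor use is shown separately. None of these restricts the target rate by baseline.

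A reader might infer three stronger things that the documents do not support:
- That the rate is known to overstate. Without a baseline distribution, the documents show only that patients below 6.5% can be enrolled, not that they were or how many.
- That one planned group is currently on a DPP-4 inhibitor and well controlled. The SAP refers to use before Trajenta; it says nothing about current use or control.
- That a confounded comparison of the two DPP-4 inhibitor groups is planned. For this rate, SAP sections 6.2 and 7.3 plan only percentages within each group, with no test or difference. Protocol sections 7.1 and 7.2 describe the analyses as descriptive, with no hypothesis tested.

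**Conclusion.** The point holds as a matter of interpretation and reporting. Nothing in the eligibility criteria, analysis sets or reporting groups separates patients who were below 6.5% at baseline from those who got there, and no planned table lets a reader do so. Under the stated assumptions, the planned rate lies 2.5 to 14 percentage points above the rate among patients not at target at baseline. That range is illustrative, because b, s and c are not in the documents. Any difference between the displayed DPP-4 inhibitor groups may partly reflect baseline mix, though no formal comparison is planned.

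The consequence is limited. This is one of several other endpoints under a secondary objective, in a study whose primary objective is safety, and it drives neither a hypothesis nor the sample size. A supplementary analysis is worth adding because it is cheap and lets the rate answer the question its name asks.

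**What to change.** Keep the protocol endpoint. In SAP sections 6.2 and 7.3, for each of the five reporting groups, add:
- the same rate among patients with baseline HbA1c of at least 6.5%, with its denominator;
- the number with baseline HbA1c below 6.5%, and how many of them were still below at last visit;
- the number who cannot be classified because the baseline value is missing.

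Label the existing figure as the proportion below 6.5% at last visit. Protocol sections 5.2.2 and 6.2.2.1 already call for HbA1c within one month before baseline, so no new data collection is required, and no change to the protocol endpoint is needed. The cost is a few rows per group and a restricted rate that is likely to look less favourable than the unrestricted one.
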